This phase of the study will be conducted in English and Spanish depending on the language of preference by the participant.

We will enroll participants who meet the inclusion criteria stated in above section. We will screen about 950 participants and enroll about 300 participants. Participants are capable to provide consent for their participation. All the RAs are CITI certified.

The study has a duration of 12 months and involves a brief telephone pre-screening, 3 home-based assessment visits (baseline, 6 months and 9 months), 3 home-based training sessions, 3 telephone check-in calls (10 days post 1st home training session, 3 months, and 7 months), and 1 brief telephone follow-up (12 months). The study will be conducted in English and Spanish. We will obtain the approval of the English material first, then submit a forward and backward translation in order to seek the approval of the Spanish material.

Eligible participants will receive a tablet with internet connection until month 9th (after the follow-up). They will be working one-on-one with a RA throughout the study. They will randomly assigned to the Tablet Condition or the PRISM 2.0 system condition. Those in the PRISM 2.0 system condition will have their tablet pre-loaded with an app that we developed. This is the app that we have been evaluating and testing in previous phases. Those in the Tablet condition will have a brand new tablet with the native apps that are in the tablet. Participants will receive \$30 for completing each assessment and \$20 for completing the telephone follow-up. They will receive a total of \$110 of financial compensation. Participants will also be able to keep the tablet at the end of the study if they choose to.

As part of the study, we will be collecting participant usage data in the tablet. The data collection will include counts of different activities in the tablet. For example, how many times they visited the Learning feature? How many times they Skyped with family members? How many times they accessed Social media sites (e.g., FaceBook, Instagram, etc)? We will not collect any identifying information.

Recruitment/Pre-screening:

Upon the approval of the study promotional material, we will display and distribute material in the Assisted Living Facilities (ALFs) and independent living facilities, and community. In order to get the support from the facilities, we will be visiting them and present the study to the stakeholders of the facilities.

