Eligible participants will continue with rest of the assessment – see Part 2 Assessment booklet. We will split this part of the assessment in multiple visits if necessary or if the participant makes the request. The sequence of administering these tests might vary and it can be altered at the discretion of the RA and/or upon the request of the participant. The assessment consists of perceptual questions about participant's social support, social network, physical and emotional well-being, and quality of life. Other questions are related to participant's ability to remember words and understand written sentences, and follow instructions. The assessment is multimodal - paper and pencil, verbal, interactive using a computer-tablet. Some instructional words will be adapted accordingly when tests are administered on a computer-tablet instead of in paper and pencil. For example, instead of circle/mark the correct answer, it might read select/choose the best answer. The RA will paraphrase the instruction statements accordingly so the participant understands it. For the quality assurance and adherence to protocol, the assessment will be audio recorded. No recording will be done if participant refuses to give consent for the recording. Breaks will be provided as needed.

Participants will be provided a booklet of assessment – see Part 1 Assessment booklet – for them to complete it before the next visit. This booklet has socio-demographic questions, technology and internet experience, proficiency with computers, etc. The RA will collect and review the answers in the next home visit.

The first home visit will end by asking the participant to enter or open a gmail account in the tablet that they will be using as part of the study. All eligible participants will receive a tablet with internet connection for the duration of the study.

Training sessions (3 home-based training sessions):

Eligible participants regardless of their randomization condition (Tablet or PRISM 2.0 system) will receive 3 home-based training sessions to learn to use the tablet and the PRISM 2.0 system. Each of the training sessions will last between 60 – 90 minutes. Breaks will be provided accordingly. These sessions are interactive and involves a lot of practice (see the training scripts attached in eProst). The training scripts are NOT intended to be followed verbatim. These are

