This phase involved randomly assigning participants to the Tablet condition or PRISM 2.0 system condition. There will be 3 data points for each participant. The design is a 3 (Residence Type) x 2 (Intervention) x 3 (Three Measurement Points) between-within groups design with two between subjects factors and one within subjects factor. The between subjects factor is Residence Type (Rural, Senior Housing, Assisted Living Facility [ALF]/Independent housing) and Intervention (PRISM vs Tablet Only). We will use confirmatory factor analysis to test for the existence of two latent constructs: social support/connectivity and loneliness. We will also use confirmatory factor analysis to test for the existence of two latent constructs psychological well-being and perceived isolation. For each, a linear growth model using mixed-effects will be estimated to examine both, whether there are differences in rates of change between intervention conditions and whether there are mean differences at specific times. The primary test will be the contrast for mean differences at the 9-month assessment. We will also examine whether differences exist at month 6. As noted in the power, we will examine residence-type differences in the intervention impact over time and if apparent, then test within residence-type. Also, if the intervention significantly impacts both social support and wellbeing, we will also test whether social support mediates the effect of the intervention on wellbeing. The mediation model estimates the effect of the intervention on the social support (path a) and the effect of the mediator on the well-being (path b). There is significant mediation if the product of these two paths ($a \times b$) is greater than zero. Statistical significance will be assessed using bias-corrected bootstrap confidence intervals on the product terms, the most powerful test of mediation. Because slopes of growth curves are calculated on concurrent times, there is not temporal precedence between growth curves on the same time frame. We will reformulate the change model in a cross-lagged panel framework to examine temporal effects in the mediation models. In the primary hypothesis tests, if we find significance for any of the latent constructs we will decompose these effects into their constituent parts. Under other aim, will utilize the same linear latent growth curve approach but the dependent measures will be: computer attitudes, and proficiency and technology uptake. We realize that there will be mediators as well as moderators (e.g. gender, ethnicity) on particular analyses, which will can be incorporated into the model using Mplus. We will obtain information on usage data on the PRISM system over time, perceptions regarding the usefulness and usability of the system and interface design issues using standard questionnaires developed during PRISM.

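### The primary month-9 difference and the month-6 difference are read off a straight line through 0, 6 and 9 months, so each is biased for its own visit unless the arm difference grows linearly

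*Combined protocol and SAP*

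**What the plan says.** The analysis paragraph of section 7 (Data Management, Phase 3) names one model for each latent construct: "a linear growth model using mixed-effects will be estimated to examine both, whether there are differences in rates of change between intervention conditions", and also "whether there are mean differences at specific times". It continues: "The primary test will be the contrast for mean differences at the 9-month assessment", then "We will also examine whether differences exist at month 6". Section 5 places the three assessments at baseline, 6 months and 9 months.

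Two later sentences in the same paragraph bear on what linear means. The mediation text begins "Because slopes of growth curves are calculated on concurrent times", and the text on computer attitudes, proficiency and uptake says the analysis "will utilize the same linear latent growth curve approach". No quadratic or piecewise term, freed time score, visit factor, check of linearity or residual covariance structure is given.

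**The concern.** A linear growth model has one intercept and one slope per arm, so the arm difference is described by two numbers. The trial can show three differences (d0, d6, d9 at baseline, 6 and 9 months). Randomisation makes d0 zero in expectation but says nothing about the ratio of d6 to d9. When that ratio is not the one a straight line imposes, the model moves part of the month-6 result into the month-9 estimate and the reverse.

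This affects the primary test. The same section makes further work depend on significance: breaking a construct into its component measures, and testing mediation if both social support and wellbeing are affected. A distorted month-9 result would carry into both. The month-6 contrast, which ought to show whether an effect is early, late or fading, comes from the same two parameters and cannot do so independently.

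Curvature common to both arms cancels from the difference. Only the shape of the arm difference matters.

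**Working it through.** **Inputs from the documents.** Visits at t = 0, 6, 9 months (section 5). Straight-line model with contrasts at months 9 and 6 (section 7). About 300 enrolled (sections 5 and 15). The documents give no SD, correlation, allocation ratio, loss, alpha or power, so there is no stated figure to reproduce.

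**Weights.** The mean of t is 5 and the sum of squares is 25 + 1 + 16 = 42. With free intercepts, and either a random intercept/slope model with equal residual variances or compound symmetry, the fitted difference at time s gives visit t the weight 1/3 + (s − 5)(t − 5)/42:

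- month 9: −1/7 d0 + 3/7 d6 + 5/7 d9
- month 6: 3/14 d0 + 5/14 d6 + 6/14 d9

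With d0 = 0, the bias is (3 d6 − 2 d9)/7 at month 9 and −3(3 d6 − 2 d9)/14 at month 6. Both vanish only if d6 = (2/3) d9. These fractions need no SD, sample size or alpha.

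| True (d0, d6, d9) | Fitted month 9 | Fitted month 6 |
|---|---|---|
| linear (0, 2d/3, d) | d | 0.67d |
| plateau (0, d, d) | 1.14d (+14%) | 0.79d (−21%) |
| (0, 0.8d, d) | 1.06d (+6%) | 0.71d |
| (0, 0.5d, d) | 0.93d (−7%) | 0.61d |
| late (0, 0, d) | 0.71d (−29%) | 0.43d (truth 0) |
| faded (0, d, 0) | 0.43d (truth 0) | 0.36d (truth d) |

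**Dependence on the fitted model.**

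- Baseline means constrained equal, correlation 0.6: month 9 becomes 1.10d for the plateau, 0.79d for late and 0.31d for faded.
- Autoregressive covariance fitted, correlation 0.5 to 0.8 over 9 months: month-9 bias is small (plateau +2% to +4%, faded 0.05d to 0.13d). Month 6 is then badly wrong: 0.05d to 0.13d for the faded shape where the truth is d, and 0.58d to 0.63d for the late shape where the truth is 0.

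**Error and power.** Assumed: 1:1 allocation and 15% loss, so 300 × 0.85 / 2 ≈ 128 per arm; SD 1; compound symmetry 0.6; two-sided 5%.

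- The squared month-9 weights sum to 35/49 = 5/7, so the variance factor is 0.6 + 0.4 × 5/7 = 0.886 and SE = √(2 × 0.886/128) = 0.118. With visit as a factor, SE = √(2/128) = 0.125.
- Rejection probability is P(|Z + b/SE| > 1.96), where b is the fitted difference.
- Faded effect of 0.3 to 0.4 SD: b = 0.129 to 0.171, so month-9 rejection is 19% to 31%. With a common baseline it is 16% to 25%. With an autoregressive covariance fitted it is 5% to 7%. If the data are autoregressive but a random intercept/slope model is fitted, the SE is 0.126 and rejection is 17% to 27%. Across 105 to 150 per arm and compound-symmetry correlation 0.4 to 0.8, the free-intercept range is 16% to 37%.
- Late effect of 0.3 to 0.4 SD: month-9 power is about 45% to 68% with the line, against 67% to 89% with visit as a factor. A month-6 effect that does not exist is declared in 22% to 36% of trials.

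**Simulation.** Random intercept/slope fit, 400 runs per setting, d6 = 0.4, d9 = 0: the mean month-9 estimate was 0.17 whether the true covariance was compound symmetry 0.6, autoregressive 0.5 or autoregressive 0.8, and rejection was 29%, 29% and 25%. With no effect at any visit, rejection was 4.5% to 5.8%.

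**The case against.** **Ambiguity.** The plan gives no model equation or time coding, and section 7 describes the design as having a three-level within-subject factor. Linear could mean a linear mixed model with categorical visits, and the two supporting phrases come from the mediation text and from another aim. This is a fair caution, but the factor sentence describes the design. The sentence naming the analysis asks about rates of change, and the later growth-curve wording matches it. If categorical visits were intended, the text still needs the same correction. The section also points to a power section that is not in the document, so any assumption made there about the time course cannot be seen.

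**Extreme shapes.** Participants keep the tablet and connection to month 9 and get a check-in call at month 7, so complete loss of effect between months 6 and 9 is not the obvious expectation. For the milder shapes (+6%, −7%) and a 0.3 SD effect, the bias is about 0.02 SD, under one-fifth of the standard error. This stands as a limit on the likely size.

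**Accuracy trade-off.** For a plateau of 0.3 SD, the line's root mean squared error at month 9 is √(0.043² + 0.118²) = 0.125, equal to the standard error with visit as a factor. The line is more accurate for the milder shapes and worse for late and faded ones. This is also true. But a primary contrast at a named visit should be estimated without depending on an untested shape, and the precision given up is small.

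**Common baseline.** With baselines constrained equal, late-effect power is about 70% to 91% against 85% to 98%, a loss of roughly 6 to 15 points instead of 21 to 23. That is correct. However, the fitted month-6 difference is then exactly two-thirds of month 9 with the same test statistic, so a late-only effect is declared at month 6 just as often as at month 9.

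**Covariance.** A fitted autoregressive structure nearly removes the month-9 bias. The plan does not specify one, so it cannot rely on that, and month 6 remains wrong.

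**Conclusion.** The concern holds. As written, both contrasts come from a straight-line model, and each is unbiased for its own visit only when the month-6 effect is two-thirds of the month-9 effect. Nothing in the document supports that ratio, and the bias can go either way.

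Under a random intercept/slope or compound-symmetry fit with free intercepts, month-9 bias runs from +6% or −7% for mild departures to +14% for a plateau and −29% for a late effect, and a fully faded effect is still estimated at 0.43d. These fractions follow from the visit times alone. The rejection and power figures rest on assumed SD, correlation, allocation and loss. The size at month 9 also depends on the covariance fitted. The overall null is safe: with no arm difference at any visit, the error rate is 5%. Confidence is medium, because the time coding is never written out.

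**What to change.** For the primary month-9 contrast and the month-6 contrast, state that visit enters as a three-level factor (baseline, 6, 9 months) with arm-by-visit terms and an unstructured covariance, and read each difference directly from that model. Keep the linear growth model for the secondary question about rates of change, and say so.

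The cost is analysis wording and one extra time parameter per arm, with no new data. If the effect truly is linear, the month-9 standard error rises from 0.118 to 0.125 SD, about 6% (128 per arm, compound symmetry 0.6, both assumed). Constraining baseline means equal, which randomisation supports, brings the visit-factor standard error to √(2 × (1 − 0.36)/128) = 0.100. That is smaller than the unconstrained line, and compares with 0.095 for a line under the same constraint.
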